Title: Preventing Weight Gain and Unhealthy Behaviors in Children

08/08/2019

D8. Power Considerations, Statistical Design, and Missing Data. The SDM Core assisted the PI with respect to the analytic plan described in this application. The SDM Core will assist the research team with the codebook (for raw data and constructs), specification of missing data flagging and procedures, data entry/capture, data management, preliminary examination of distributions in preparation for analyses, conduct of statistical analyses, and assistance in interpretation of programming output. All analyses will be completed by the SDM Core which will have individuals with extensive expertise in the statistical models required for analyzing the data collected in the proposed project.

D8.1. Power Considerations. The power analysis was performed using G*Power (v.3.1.7) to determine the smallest effect detectable assuming a sample size of 80 participants, power of 0.80, correlation between measures of 0.80, and alpha of 0.05. The study is sufficiently powered to detect a Cohens *d* effect size of 0.20, considered a small effect. Previous large scale longitudinal studies of school year vs. summer weight gain,[12, 14, 36] studies that have provided a structured program to children during the summer,[129, 130] and pilot work have shown that the Cohens *d* effect size of the difference between conditions should be approximately 0.50. Children not receiving the Voucher Program are estimated to experience a mean increase in z-BMI of 0.22 over the summer. Conservatively, children in the Voucher Program are estimated to experience half of the gain in z-BMI during the summer of children not in the Voucher Program (i.e., 0.11 increase in z-BMI). The difference between z-BMI change for children who receive a voucher and do not receive a voucher (i.e., 0.22 vs. 0.11) is equivalent to a Cohens *d* of 0.46. However, the power to detect a small effect was chosen to ensure that the study is able to detect the effect of the primary and secondary outcomes.

D8.2. Statistical Models. To test the Aims, analytical modeling that capitalizes on the richness of the data set will be utilized. To test the hypothesis in Aim 1, repeated measures linear and non-linear mixed models accounting for repeated measures within children and children within schools will be estimated. Group, time, setting (i.e., school vs. summer) and all 2-way and 3-way interactions will be included, with the group-x-time-x-setting interaction as the primary contrast of interest. For Aim 2, the differences in obesogenic behaviors over time will be evaluated using the same repeated measures linear and non-linear mixed models. Structural equation models will be estimated to evaluate the mediating pathways of the obesogenic behaviors on the amount of change occurring in zBMI over time between the two groups.

D8.3. Sex as a Biological Variable. Because girls and boys have been shown to engage in differing levels of obesogenic behaviors and to have differing levels of fitness and prevalence of overweight and obesity, all models will include sex (i.e., boys vs. girls) and age as covariates. Including sex as a covariate in models will preserve the statistical power of the study while allowing for the examination of sex as a biological variable.

D8.4. Missing Data. Across this study, four scenarios with missing data are possible: 1) missing items within children; 2) missing cases (i.e., children not present to complete assessments); and whether the missingness is for 3) missing determinants/covariates or 4) missing outcomes (e.g., zBMI, physical activity). For missing assessments, such as incomplete diaries, parent surveys, accelerometer data, or BMI, the parents will be contacted and, where willing, they will be invited to re-complete the missing assessments. Where children are not present at the school on days of BMI assessments or to pick-up their monitor and surveys, data collectors will return to the camp on another day to complete the assessments. For any assessments not obtained, models will be estimated using full information maximum likelihood estimators, as well as employ multiple imputation techniques. These two strategies for handling missing outcome data will be compared (analogous to a sensitivity analysis) to determine the most appropriate way to handle the missingness. Based on previous large-scale group randomized trials,[102, 131] full information maximum likelihood estimators provide a robust and unbiased estimate. This is consistent with literature comparing this estimator to models using multiple imputation.[132] For missing determinant/covariates that are continuous, multiple imputations will be employed. For missing determinant/covariates that are categorical, a missing dummy variable technique will be used rather than imputing categorical data.[133, 134]

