Figure D6. Schedule of school year and summer measurements

Abbreviations—body mass index (BMI), cardiorespiratory fitness (CRF)

D6. Primary and Secondary Measures. Details for implementation of the measurement plan will be finalized in consultation with the CTL Core with respect to training of data collectors, record-keeping procedures, data capture procedures, and construct scoring. For a detailed description of the primary, secondary, covariate, predictor, and determinant measures see Clin-Trls Section 4, Narrative Study Description and Outcome Measures. All measures were selected in consultation with our consultants, the participating school district, and the Recreation Commission. The measures selected 1) represent state-of-the-art techniques that are known to produce valid and reliable data and 2) minimize burden on the participating families.

D6.1. Primary Outcomes (Specific Aim 1). All students enrolled in the study will take part in a cardiovascular fitness (CRF) test (i.e., PACER)[2-8] and have their height and weight measured by trained research staff using standard procedures during a regularly scheduled physical education class. This information will be used to compare changes in BMI (translated into age-sex z-scores [zBMI]) and CRF during summer and the school year. The tests are valid and reliable and used extensively with the proposed age groups.[59-63] Peak height velocity will also be collected as a marker of biological maturation (covariate in statistical models).[1]

D6.2. Secondary Outcomes (Specific Aim 2). Briefly, physical activity, sedentary behaviors, and sleep will be collected using a non-dominant wrist-placed ActiGraph Link for 9-days (common timeframe to collect physical

activity data).[45, 64-74] Children's screen time will be assessed using a parent-proxy report measure completed daily for 9 days by the parent with their child. Parents/children will estimate the total amount of time (hours and minutes) spent in front of a screen that day (e.g., TV, computer, video-game, smartphone, and tablet). [75] Dietary behavior of participants will be estimated using several dietary screeners that have been found to be valid and reliable when compared to multiple pass dietary recall.[76-90]

Table D6. Description of Measures for Primary and Secondary Outcomes and Exploratory Variables at the Child Level

Outcome	Construct	Assessment/Tool	Description/Protocol

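### SAP D8.1 compares a detectable d of 0.20 with an expected d of 0.46 that are not on one scale; between two arms of 40, neither set of inputs gives adequate power for a 0.11 zBMI difference

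*SAP*

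**What the plan says.** SAP D8.1 describes a G*Power calculation of the smallest detectable effect, "assuming a sample size of 80 participants, power of 0.80", with a "correlation between measures of 0.80, and alpha of 0.05". It reports: "The study is sufficiently powered to detect a Cohens *d* effect size of 0.20, considered a small effect". It names the software but not the test.

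The same paragraph then gives the expected effect. "Children not receiving the Voucher Program are estimated to experience a mean increase in z-BMI of 0.22 over the summer", and voucher children are expected to gain half of that, 0.11. The SAP converts this contrast to a standardised effect of 0.46, in a sentence that begins: "The difference between z-BMI change for children who receive a voucher and do not receive a voucher (i.e., 0.22 vs. 0.11) is equivalent to". No SD is given for zBMI or for its change, and the SD that standardises d is not named. The paragraph closes with a claim about both classes of outcome: "the power to detect a small effect was chosen to ensure that the study is able to detect the effect of the primary and secondary".

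Protocol D8.1 repeats that the study has enough power on the basis of 0.22 versus 0.11. Protocol D6.1 defines the outcome as BMI converted to an age-sex z-score. Protocol D9 randomises individual children to two conditions in equal numbers, so 80 children means 40 per arm.

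**The concern.** The argument for adequate power is that 0.20 lies below 0.46. That works only if both values are multiples of the same SD and refer to the same comparison, and the SAP does not show that they do.

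One sign that they do not is the SD implied by 0.46, which is 0.24. For an outcome on a z-score scale, that is plausible only as the SD of a change between two very highly correlated measurements. The correlation used for the 0.20 is 0.80, which at a z-score SD near 1 gives a much larger change SD. A second sign is that 0.20 is very small for a comparison of two groups of 40.

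At stake is the main quantitative claim about the primary zBMI outcome, which appears in both documents. A reader would take a null result on zBMI as informative when the trial may have had little chance of detecting the planned difference.

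**Working it through.** **Inputs from the documents.** N = 80, power 0.80, r = 0.80, alpha 0.05, detectable d = 0.20, changes of 0.22 and 0.11 (difference 0.11), expected d = 0.46 (all SAP D8.1); two equal arms, so 40 per arm (protocol D9). **Assumptions.** Two-sided alpha, because sidedness is not stated, and a zBMI SD of 1.0 with range 0.8 to 1.2, because no SD is given.

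**1. Reproduce the 0.20.** For a within-between interaction with 2 groups and m = 2 measurements, the noncentrality is f² × N × m / (1 − r), with 1 and 78 degrees of freedom.
- 80% power needs f = 0.1003, so 2f = 0.2006. Check: 0.1003² × 80 × 2 / 0.20 = 8.05.
- A paired t test on all 80 children gives the same number: 0.317 × sqrt(2 × 0.20) = 0.2006.
- Three or four measurements give 2f = 0.18 or 0.17, so the two-measurement form fits best.

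**2. What that 0.20 means between arms.** In a 2 × 2 interaction each cell departs by f SDs, so the difference in change between arms is 4f = 0.40 cross-sectional SDs. The change SD is SD × sqrt(2(1 − r)) = 0.632 SD at r = 0.80, and 0.40/0.632 = 0.63 change-SDs. A two-sample t test on change scores with 40 per arm also gives 0.634. So the stated 0.20 is the same requirement as 0.63 change-SDs.

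**3. What the 0.46 means.** The implied SD is 0.11/0.46 = 0.239. Read as a change SD, d = 0.46 should be compared with 0.63, not 0.20. Conversely, at r = 0.80 an effect of 0.46 change-SDs is 0.46 × 0.632 / 2 = 0.145 on the scale of the 0.20. On either common scale the expected effect is below the detectable one.

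**4. Can r = 0.80 and d = 0.46 describe the same zBMI data?** Use d = 0.11 / (SD × sqrt(0.40)) and required r = 1 − 0.239² / (2 × SD²).

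| zBMI SD (assumed) | Change SD at r = 0.80 | d for 0.11 | r needed for d = 0.46 |
|---|---|---|---|
| 0.8 | 0.506 | 0.22 | 0.955 |
| 1.0 | 0.632 | 0.17 | 0.971 |
| 1.2 | 0.759 | 0.14 | 0.980 |

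They agree only at SD = 0.239/0.632 = 0.38. If 0.239 were instead the cross-sectional SD, it would be further still from 1.

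**5. Power for 0.11, 40 per arm, two-sided 0.05, change-score comparison.**

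| Input kept | Effect in change-SDs | Power | Detectable difference at 80% power |
|---|---|---|---|
| d = 0.46 as a change-scale effect | 0.46 | 53% | 0.634 × 0.239 = 0.15 zBMI |
| r = 0.80, SD 1.0 | 0.17 | 12% | 0.634 × 0.632 = 0.40 zBMI |
| r = 0.80, SD 0.8 | 0.22 | 16% | 0.634 × 0.506 = 0.32 zBMI |
| r = 0.80, SD 1.2 | 0.14 | 10% | 0.634 × 0.759 = 0.48 zBMI |

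Adjusting for baseline changes little. At SD 1.0 the residual SD is sqrt(1 − 0.80²) = 0.60, 0.11 is 0.18 of it, and power is 13%.

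**The case against.** The strongest reply is that the documents contain no contradiction. They give no zBMI SD. A z-score has SD 1 in its reference population, not necessarily in children from these schools. The SAP never says that 0.80 is the zBMI correlation: it may be one generic value for all outcomes, with 0.46 taken separately from pilot or earlier studies. If the true zBMI correlation is near 0.97, then 0.80 is conservative for that outcome.

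Much of this stands. A reader might infer that 0.80 and 0.46 cannot both be right, or that 0.80 is wrong. The documents do not support either inference; the conflict depends on the assumed SD. An SD of 0.38 would reconcile the figures, although nothing in the documents points to so narrow a spread.

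The reply does not rescue the power claim. If the two figures rest on different variance assumptions, comparing 0.20 with 0.46 is not like with like. The 53% needs no outside SD; it only takes the plan's own 0.46 as a change-scale effect. A correlation of 0.97 does not help either. It would turn the 0.20 into 0.08, which might be read as comfortably below 0.11, but that is again twice f and not a between-arm difference. At r = 0.97 and SD 1.0 the change SD is sqrt(0.06) = 0.245, the between-arm detectable difference is 0.634 × 0.245 = 0.155 zBMI, and power for 0.11 is about 51%.

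It is also fair that protocol D12 presents the study as preliminary to a larger trial, so modest power is defensible. The statement that power is sufficient is not.

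**Conclusion.** The point holds as a fault in the power statement. The detectable 0.20 and the expected 0.46 are on different scales, and their comparison does not show that the study can detect 0.22 versus 0.11. Power for that difference is about 53% if d = 0.46 is kept as a change-scale effect, and about 12% (16% to 10% for SD 0.8 to 1.2) if r = 0.80 is kept with SD 1.0. The matching detectable differences are about 0.15 and 0.40 zBMI.

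The 53% assumes 40 per arm, two-sided 0.05, a simple comparison of summer change and no attrition. The 12% also assumes the SD. That the 0.20 came from a two-measurement interaction is inferred from the match, since the SAP does not name the test. The planned mixed model with a three-way interaction was not itself powered here.

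The closing sentence on primary and secondary outcomes has no support beyond zBMI: D8.1 gives no correlation or expected effect for PACER or any behaviour. A reader might go on to conclude that those outcomes are underpowered, but the documents give no figures from which to show that.

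**What to change.** In SAP D8.1:
- say which SD standardises d, and name the test behind the calculation;
- state one consistent SD and correlation for zBMI, taken from the pilot or longitudinal data already cited;
- recompute, for 40 versus 40, the detectable difference in zBMI units and the power for 0.11;
- do not replace 0.20 with the 0.08 that r = 0.97 would give;
- limit the closing sentence to zBMI, or give the correlation, expected effect and detectable effect for PACER and each behaviour.

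Restate the power claim in SAP D8.1 and protocol D8.1 to match. Keep n = 80.

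The cost is a recalculation and revised wording in two documents, with no extra children and no change to procedures. The downside is that the stated power becomes less favourable.

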[figure not shown]

Title: Preventing Weight Gain and Unhealthy Behaviors in Children

08/08/2019

Rigor and Transparency. The proposed study is designed to rigorously evaluate the effect of providing access to structured programs during the summer on children's unhealthy weight gain, fitness loss, and the obesogenic behaviors that underlie these effects. Specific examples of the rigor of this study include randomizing children following baseline measurement, using measures shown to produce valid and reliable data in the study population, completion of a power analysis, appropriate statistical analyses, properly controlled design, and blinding staff handling the data to study condition. These methods will allow for the proposed study to produce robust and unbiased results.

D1. Theoretical/Conceptual Framework - Structured Days Hypothesis. This study hypothesizes that summer camps will provide structure during the summer that will reduce children's obesogenic behaviors. Mechanisms driving reduced obesogenic behaviors on structured days are detailed in **Figure D1** below.

D2. Hypotheses.

Aim 1 (Primary): It is *hypothesized* that **A**) children randomized to attend the summer day camp will experience minimal gain in zBMI and loss of fitness during the summer that they receive summer camp access; **B**) children will experience accelerated weight gain and fitness loss during the summer they are randomized to not receive summer camp access and that **C**) all children will experience similar weight loss and fitness gain during the school year due to the restrictive, compulsory, and regulatory components of school.

Aim 2 (Secondary): It is *hypothesized* that **A**) children randomized to attend the camp will engage in fewer obesogenic behaviors during the summer that they attend the camp than their peers during the summer they do not attend camp, and that **B**) all children will engage in fewer and similar levels of obesogenic behaviors during the school year due to the restrictive, compulsory, and regulatory components of school.

Aim 3 (Exploratory): It is of interest to explore: **A**) if children randomized to attend the camp will experience increases in self-regulation while their peers who do not attend the camp will experience decreases in self-regulation, and if **B**) self-regulation at the beginning of summer will moderate unhealthy changes in weight and fitness at the end of the summer for those children who do not attend the summer camp.

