D3. Study Design. The study will be a randomized controlled trial. To distribute costs over years, the study will recruit two cohorts of 1st and 3rd grade students. The first cohort will be recruited in Y01 and the second will be recruited in Y02. Following baseline data collection, children in each cohort will be randomly assigned to either the treatment or control. The sample of students recruited in the 1st grade will be observed during the summer after their 1st grade year and the school year when they are in the 2nd grade. Students recruited from the 3rd grade will be observed in the summer following their 3rd grade year and the school year during 4th grade.

D4. Study Population and Recruitment. Procedures for sampling children are detailed in **Clin-Trls Section 2, Recruitment and Retention Plan**. Briefly, the Recreation Commission operates 11 summer day camps located

at parks. Each camp serves ~100 children every summer. To draw a sample of children, 5 summer camps that operate in the catchment area of elementary schools where $\geq 90\%$ (range = 90%, 100%) of children enrolled are eligible for free and reduced lunch have been identified. A total of 2,333 children (49% female) attend these schools. Children attending the identified schools will be stratified by gender and grade level. In Y01 and Y02, 40 (i.e., 80 total) randomly identified children will be invited to participate in the study.

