D8.2. Statistical Models. To test the hypothesis in **Aim 1** and **Aim 2**, repeated measures linear and non-linear mixed models accounting for repeated measures within children and children within schools will be estimated. Group, time, setting (i.e., school vs. summer) and all 2-way and 3-way interactions will be included, with the group-x-time-x-setting interaction as the primary contrast of interest. Structural equation models will also estimate the mediating pathways of the obesogenic behaviors on zBMI change.

D8.3. Sex as a Biological Variable. Because girls and boys have been shown to engage in differing levels of obesogenic behaviors and to have differing levels of fitness and prevalence of overweight and obesity, all models will include sex (i.e., boys vs. girls) and age as covariates. Including sex as a covariate in models will preserve the statistical power of the study while allowing for the examination of sex as a biological variable.

D9. Group Assignment. The unit of randomization will be at the child level. The two conditions will be: 1) Intervention - children receiving a voucher for a summer day camp and 2) Control - no summer day camp voucher. Children will be randomized (using a random number generator) by stratifying them based on grade and gender to ensure equal numbers across the age range and boys and girls in each of the two conditions.

D10. Timeline. A project timeline is provided in Clin-Trls Section 2, Extended Study Timeline.

D11. Limitations and Benchmarks of Success. One key to success will be the study retention of children/families over time. To address this, the measures have been modified based on piloting with comparable individuals and incentives are planned for participation. Another key issue is whether children receiving vouchers attend the day camp during the designated summer. Children in the intervention condition who fail to attend the camp would obviously not be exposed to the independent variable. However, the Recreation Commission has observed that high community demand for summer programming, coupled with ease of access because the camp is centrally located, makes attendance likely. Further, camp attendance (and lack thereof) will be tracked to explore possible barriers to attendance.

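### SAP D8.1 claims 80% power for d = 0.20, but the parallel 40 v 40 design detects a difference in summer change of about 0.63 SD of change (0.40 raw SD), and the SD behind d = 0.46 is not named

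*SAP*

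**What the plan says.** SAP D8.1 reports a G*Power calculation of the smallest detectable effect, "assuming a sample size of 80 participants, power of 0.80, correlation between measures of 0.80, and alpha of 0.05", and gives the answer as a Cohen's d "effect size of 0.20, considered a small effect". It then describes the expected effect: "The difference between z-BMI change for children who receive a voucher and do not receive a voucher (i.e., 0.22 vs. 0.11") is put at d = 0.46. It closes by saying that power for "a small effect was chosen to ensure that the study is able to detect the effect of the primary and secondary outcomes". Protocol D8.1 calls the study sufficiently powered for 0.22 v 0.11.

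On design, Protocol D3 says "children in each cohort will be randomly assigned to either the treatment or control", with each child followed over one summer and one school year. Protocol D9 stratifies the randomisation "to ensure equal numbers across the age range and boys and girls in each of the two conditions". The Aim 1 hypothesis in Protocol D2 reads differently: "children will experience accelerated weight gain and fitness loss during the summer they are randomized to not receive summer camp access", as though each child had one summer with camp and one without. SAP D8.2 specifies the analysis "with the group-x-time-x-setting interaction as the primary contrast of interest".

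Neither document gives the G*Power test family, the sidedness of alpha, or the SD that standardises 0.20 or 0.46.

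**The concern.** A detectable d of 0.20 with 40 children per arm is far smaller than a two-group comparison normally gives. A correlation of 0.80 between measures helps, but not by that much. If 0.20 belongs to another test or another scale, three things follow.

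- The assurance about small effects in the primary and secondary outcomes has no basis. Null secondary results could then be read as evidence against small effects that the trial had little chance of finding.
- The comfortable gap that the SAP implies between 0.20 (detectable) and 0.46 (expected) may be narrow or absent.
- Protocol D8.1's statement of sufficiency for the primary outcome depends on an SD that is not given.

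**Working it through.** **Inputs.** N = 80, power 0.80, correlation ρ = 0.80 and alpha 0.05 (SAP D8.1). Two conditions in equal numbers (Protocol D9), hence 40 v 40; this split is inferred from the total of 80. Two-sided testing is assumed. Expected difference in change: 0.22 − 0.11 = 0.11 zBMI, put at d = 0.46 (SAP D8.1).

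**Scales.** For two measurements with a common raw SD σ:
- SD of change = σ√(2(1 − ρ)) = σ√0.40 = 0.632σ.
- Residual SD after baseline adjustment = σ√(1 − ρ²) = σ√0.36 = 0.600σ.

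**Step 1: reproduce 0.20.** Two calculations give it.
- Paired t-test in all 80 children (noncentral t, 79 df): detectable effect 0.3171 SD of change, and 0.3171 × 0.632 = 0.2006 raw SD. This has no control group. It fits the within-child wording of Aim 1 but not D3 and D9.
- Repeated-measures group-by-time interaction, 2 groups × 2 times, noncentrality λ = f²·N·m/(1 − ρ) with m = 2: detectable f = 0.1003, so 2f = 0.2006. In a 2 × 2 layout each cell departs by ±fσ. One group's change therefore shifts by +2fσ and the other's by −2fσ, and the between-group difference in change is 4f = 0.401 raw SD.

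**Step 2: detectable difference for the randomised comparison.** Two-sample t on change, noncentrality δ√(40/2), 78 df, 80% power:

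| Scale | Two-sided 0.05 | One-sided 0.05 |
|---|---|---|
| SD of change | 0.634 | 0.561 |
| Raw SD, change score (× 0.632) | 0.401 | 0.355 |
| Raw SD, baseline-adjusted (× 0.600) | 0.381 | 0.337 |

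None of these is 0.20.

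**Step 3: power at 0.20, and the size needed for 80%.**

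| Meaning of 0.20 | Effect in SD of the analysed quantity | Power, 40 v 40 | Needed per arm |
|---|---|---|---|
| SD of change | 0.20 | 14% | 394 |
| Raw SD, change score | 0.20/0.632 = 0.316 | 29% | 158 |
| Raw SD, baseline-adjusted | 0.20/0.600 = 0.333 | 31% | 143 |

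**Step 4: power for 0.11 zBMI.** The implied SD is 0.11/0.46 = 0.239.
- If 0.239 is the SD of change, the effect is 0.46 SD of change and power is 53%. The implied raw zBMI SD is 0.239/0.632 = 0.378.
- If 0.239 is the raw SD, the effect is 0.46/0.632 = 0.727 SD of change and power is 89% (92% with baseline adjustment).

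The SAP attaches 0.46 to a difference between changes, so the first reading is the more natural one, but the text does not settle it.

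**Step 5: loss to follow-up.** Protocol D4 invites 80 children in total and adds none for loss. Assuming 90% or 80% retention (36 or 32 per arm), 53% becomes 49% or 44%, and 89% becomes 86% or 82%.

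**Step 6: the declared primary contrast.** Steps 1 to 5 do not address the three-way interaction, and the measurement schedule figure is not available to define it. As an illustration only, assume three equally correlated occasions and take summer change minus school-year change. Its variance is 6(1 − ρ)σ² = 1.20σ², so its SD is 1.095σ. The detectable value is 0.634 × 1.095 = 0.69 raw SD, and power at 0.46 raw SD is about 46%. Clustering by school and the presence of two primary outcomes are ignored throughout.

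**The case against.** The best defence is that 0.20 is not a miscalculation: as 2f for the 2 × 2 interaction it is correct for a parallel 40 v 40 trial on the stated inputs, and the fault is an unlabelled scale. It is true that the software arithmetic can be reproduced. But the SAP calls the figure a Cohen's d, labels it small, and sets it beside a d of 0.46 for the difference between conditions. On that footing the matching value is 4f = 0.40, and the claim fails.

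Second, Protocol D8.1 claims sufficiency only for 0.22 v 0.11, and power there may be 89%. This stands, and inadequate power for the primary outcome is not shown here. However, the two readings in Step 4 are not exhaustive. zBMI is a z-score. If its raw SD were 0.5 or 1.0 (assumed values) with ρ = 0.80, power for 0.11 would be 34% or 12%. With a raw SD of 1.0, an SD of change of 0.239 would need ρ = 1 − 0.239²/2 = 0.97.

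Third, Protocol D8.1 refers to a further section of the application for power details, and that section may name the test and the SD. It could settle the choice between 53% and 89%. It could not make 0.20 the detectable between-group difference.

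Fourth, the secondary behaviours are also measured during summer, and more occasions help: 2f falls to 0.181 with three and 0.166 with four. These are again values of 2f, not between-group differences in change. The power figures at 0.20 are for a two-occasion change with ρ = 0.80, and Aim 2 power was not calculated separately.

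Finally, Protocol D12 presents the study as preliminary. That bears on how much power is needed, not on whether the stated power is true.

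**Conclusion.** The concern holds. For the parallel design in Protocol D3 and D9, 80 children do not give 80% power for a between-group difference in change of d = 0.20. Power there is 14% to 31%, and the detectable difference is 0.63 SD of change, or 0.40 raw SD (0.38 with baseline adjustment). One-sided testing does not rescue the claim. Whether the trial is adequately powered for its hypothesised 0.11 zBMI cannot be determined from the documents: about 53% or about 89%, according to which SD gave 0.46. The stated three-way primary contrast has no power calculation at all.

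These results assume 40 per arm, two-sided 0.05, ρ = 0.80, a comparison of two-occasion change, full retention and no clustering. The last two assumptions are favourable to the plan. Because the headline power statement is wrong for the stated design, it must be corrected.

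**What to change.** In SAP D8.1, withdraw the 0.20 figure and the closing assurance about small effects in the primary and secondary outcomes. Replacement text:

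> With 40 children per arm, correlation 0.80 and two-sided alpha 0.05, a two-group comparison of summer change has 80% power for 0.63 SD of change (0.40 SD of the raw outcome). The d of 0.46 is in units of [SD of change / raw zBMI SD], for which power is [53% / 89%]. These figures do not apply to the group-by-time-by-setting contrast.

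Keep only the option that matches the SD actually used, state its value and source, and recompute if neither option applies. In addition:

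- Name the test and the sidedness, and repeat the power at the expected number of completers.
- Bring the sufficiency statement in Protocol D8.1 into line with the result.
- Reconcile the within-child wording of Aim 1 with D3 and D9, and base the power statement on the design that remains.
- Preferably add a calculation for the three-way contrast, using the actual measurement schedule.

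The cost is wording in the SAP and protocol, plus a short recalculation. Enrolment and recruitment are unaffected; the stated power becomes less favourable.
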